### **Dosing period:**

Subjects enrolled will remain outpatient. Subjects will be randomized 4:1 to receive VIR-2218 or placebo within 48 hours prior to study drug administration on Day 1. Subject eligibility must be confirmed prior to study drug administration on Day 1. Subjects will return to the clinical investigative site at Week 4 to receive a second dose of the same study drug administered on Day 1. The decision to administer a second dose will be made based on Week 3 laboratory values in accordance with dose suspension/stopping criteria in Section 4.6.

Subjects enrolled into the optional cohorts will receive VIR-2218 or placebo on Day 1 and Week 4 at a maximum dose-level of 200 mg.

### Post-dose follow-up period:

Subjects will return to the clinical investigative site on an outpatient basis for safety, tolerability, PK, and antiviral activity monitoring at specified timepoints during this Post-dose Follow-up period (Week 5 to Week 16). Additional HBsAg monitoring is required for subjects with  $a \ge 1 \log_{10}$  change from baseline (Day 1 predose level) decrease in HBsAg achieved by the Week 16 visit.

### **Extended follow-up period:**

Subjects who require additional HBsAg monitoring will return to the clinical investigational site for in-person assessments. Extended follow-up visits will occur every 4 weeks starting at Week 20, and subjects will be followed until the HBsAg level returns to > 90% of the Day 1 predose level or Week 48, whichever comes earlier. Additional HBsAg monitoring may be discontinued at the Sponsor's discretion based on emerging data.

#### 4.2. Discontinuations

Subjects who discontinue prematurely will be followed for safety, and under certain circumstances, subjects who discontinue study drug (as described in Section 4.3) may be replaced. If a subject discontinues from the study post-dose but before completion of the Week 16 visit, an Early Termination (ET) visit should be performed.

### 4.3. Replacement of Subjects

Replacement subjects may be enrolled to ensure that the minimum data requirements for SRC decisions and study progression are met, as described in Section 4.5. Subjects who do not receive the full planned dose, do not receive a second dose, discontinue due to an AE that does not meet study progression and dose suspension/stopping rules (Section 4.6), or who withdraw from the study, may be replaced with confirmation by the SRC. Subjects who are discontinued from treatment for reasons other than experiencing an AE may be replaced following discussion between the Sponsor and investigator.

The replacement subject will be assigned a unique study identification number and will receive the same study drug assignment and dose level as the subject who is being replaced and in the same blinded fashion.

### 4.4. Safety Review Committee

An SRC will perform ongoing reviews of safety, tolerability, and available study data collected throughout the study with the primary purpose of protecting the safety of subjects participating in this clinical study. The SRC will be governed by an SRC Charter that will be finalized prior to screening the first subject.

The SRC will undertake safety data review prior to initiation of dosing the optional cohorts of the study in accordance with the SRC Charter. In addition, ad hoc SRC meetings may take place as needed, e.g., for a significant safety event such as a subject or cohort stopping criterion being reached (Section 4.6).

Decisions to suspend dosing or discontinue individual subjects from study drug will be made according to predetermined stopping rules (Section 4.6). Additionally, the SRC may recommend discontinuation of the study to the Sponsor. The SRC membership composition is described in detail in the SRC Charter.

### 4.5. Study Drug Dosing and Study Progression

Progression rules are based on the absence of prespecified safety signals. Standard toxicity grading according to the current Common Terminology Criteria for Adverse Events (CTCAE) Version 5 will be used to grade AEs. The decision to enroll an optional cohort or expand an existing cohort will be made by the SRC based on available safety, tolerability, and antiviral activity data, if further data are considered necessary to better understand dose response and/or safety and tolerability.

Subjects will receive VIR-2218 or placebo via SC injection according to the schedules provided in Appendix 2.

### 4.6. Stopping Rules

The following stopping rules are based on potential safety signals. Standard toxicity grading according to the CTCAE Version 5.0 will be used to grade AEs. When a cohort is stopped, no further study drug will be administered at the dose level and further progression will be suspended. An ad hoc SRC meeting will be held, and only following SRC approval, may dosing be resumed; if required, additional approval from the concerned regulatory authority and the independent ethics committee (IEC)/institutional review board (IRB), in accordance with applicable requirements, will be obtained. De-escalation to a lower dose will be allowed at Sponsor discretion.

### 4.6.1. Cohort Stopping Rules

If any of the criteria described below are met, as determined by the Sponsor medical monitor or designee, cohort dosing will be suspended or stopped:

- If 1 or more subjects experience a Grade 3 study drug-related rash
- If 2 or more subjects experience the same study drug-related Grade 3 or higher AE
- If 1 or more subjects experience a study drug-related serious adverse event (SAE)
- If 1 or more subjects experiences a Grade 4 AE of rash, regardless of assessed causality

### 4.6.2. Individual Subject Stopping Rules

Individual subjects who have received 1 dose of study drug will not receive a second dose if any the following criteria are met:

- Serum ALT  $> 10 \times$  upper limit of normal (ULN)
- Serum ALT  $> 5 \times$  ULN, with no change (< 50% of baseline) in HBsAg
- Serum ALT or AST  $> 3 \times ULN$  with a concomitant total bilirubin  $> 2 \times ULN$
- Any clinical manifestations of hepatic decompensation including but not limited to jaundice, ascites, variceal hemorrhage, hepatic encephalopathy, spontaneous bacterial peritonitis, or hepatorenal syndrome

The investigator should contact the medical monitor in the event that any of the above criteria are met, prior to dose discontinuation, unless the investigator believes that immediate action is warranted to ensure the continued safety of the subject.

### 5. SUBJECT POPULATION

### 5.1. Number of Subjects and Subject Selection

A total of up to 30 adult subjects with chronic HBV infection without cirrhosis on NrtI therapy are planned to complete this study.

- **Part One Planned/Optional Dose Cohorts:** Up to 15 adult subjects with chronic HBV infection without cirrhosis who are HBeAg-negative on NrtI therapy
- **Part Two Planned/Optional Dose Cohorts:** Up to 15 adult subjects with chronic HBV infection without cirrhosis who are HBeAg-positive on NrtI therapy

### 5.2. Inclusion Criteria

Each subject must meet all the following inclusion criteria at screening to be eligible for enrollment in the study. All laboratory test requirements for inclusion will be performed by central laboratory:

- 1. Age 18 (or age of legal consent, whichever is older) to 65 years at the time of screening
- 2. 12-lead ECG within normal limits; or, with no clinically significant abnormalities at screening, as determined by the clinical investigator
- 3. Female subjects must have a negative pregnancy test or confirmation of post-menopausal status. Post-menopausal status is defined as 12 months with no menses without alternative medical cause. Women of child-bearing potential (WOCBP) must have a negative serum pregnancy test (using central laboratory) at screening and a negative urine pregnancy test on Day 1, cannot be breast feeding, and must be willing to use highly effective methods of contraception 14 days before study drug administration through 12 weeks after last study drug administration. Refer to Section 6.6 for more information on highly effective methods of contraception.
- 4. Male subjects with female partners of child-bearing potential must agree to meet 1 of the following contraception requirements from the time of study drug administration until the last follow-up visit: vasectomy with documentation of azoospermia, or male condom use plus partner use of 1 of the contraceptive options listed for contraception for WOCBP. Male subjects must also agree not to donate sperm for the 12 weeks following last study drug administration. Refer to Section 6.6 for more information on highly effective methods of contraception.
- 5. Agrees to not donate blood during the duration of the study
- 6. Willing to comply with the study requirements and able to provide written informed consent
- 7. Weight  $\geq$  40 kg to  $\leq$  125 kg
- 8. Chronic HBV infection as defined by a positive serum HBsAg for  $\geq 6$  months

- 9. On NrtI therapy for at least 6 months
- 10. HBsAg > 150 IU/mL
- 11. HBV DNA < 90 IU/mL
- 12. Part One only: HBeAg-negative
- 13. Part Two only: HBeAg-positive
- 14. Agrees not to increase physical activity from the time of screening through 4 weeks after final administration of VIR-2218

### **5.3.** Exclusion Criteria

Each subject must not meet any of the following exclusion criteria to be eligible for enrollment in the study:

- 1. Any clinically significant chronic medical condition other than chronic HBV infection that, in the opinion of the investigator makes the volunteer unsuitable for participation in the study
- 2. Any clinically significant acute condition such as fever (> 38° C) or acute respiratory illness within 7 days of first study drug administration
- 3. Significant fibrosis or cirrhosis as defined by having either a FibroScan result of > 8.5kPa at screening or a liver biopsy within 1 year with Metavir F3 fibrosis or F4 cirrhosis. Refer to Section 7.2.8 for more information.
- 4. Receipt of a vaccine 14 days prior to Day 1
- 5. Previous or current psychiatric condition that precludes compliance with the protocol. Specifically excluded are persons with psychoses, ongoing risk for suicide, or history of suicide attempt or gesture within the past 5 years
- 6. Systolic blood pressure > 140 mmHg and a diastolic blood pressure of > 90 mmHg after approximately 10 minutes resting at screening
- 7. Subject has the following laboratory parameters at screening by central laboratory:
  - a. Creatinine or total bilirubin above the upper limit of normal (ULN), OR international normalized ratio (INR) above 1.1x ULN
  - b. hemoglobin, ANC, platelets, or albumin below the lower limit of normal (LLN)
  - c. White blood cell (WBC), potassium, or sodium above the ULN or below the LLN
  - d. serum ALT or AST  $> 2 \times ULN$

- Study Screening laboratory tests may be repeated once (e.g., for values thought to be erroneous) with medical monitor approval.
- 8. Received an investigational agent within 90 days before study drug administration or are active in the follow-up phase of another clinical study involving interventional treatment. Subjects must also agree not to take part in any other study at any time during their participation in this study, inclusive of the follow-up period.
- 9. Used prescription drugs within 14 days before study drug administration except for a stable dose of medication to treat hypertension, inhaler or nebulizer to treat asthma, hormone replacement therapy, antihistamines, and contraceptive therapy (refer to Section 6.4.1 for more information). Hypertension must be well controlled on no more than 2 medications or 1 medication with two active components for > 6 months. Asthma must be well controlled, requiring, on average, use of a rescue bronchodilator no more than twice per week.
- 10. Use of over-the-counter (OTC) medication or herbal remedy within 14 days before Day 1 and throughout the study, with the following exceptions of permitted OTC medications: Paracetamol (acetaminophen)  $\leq 2g/day$ , aspirin  $\leq 3g/day$  or ibuprofen  $\leq 1.2 g/day$ .
- 11. Active infection with human immunodeficiency virus (HIV), hepatitis C virus (HCV) or hepatitis Delta virus as determined by the central laboratory
- 12. Consume more than 7 units of alcohol per week (unit: 1 glass of wine [125 mL] = 1 measure of spirits [30 mL] = one-half pint of beer [284 mL]). Alcohol is limited to no more than 1 unit per day for the duration of the study
- 13. History or clinical evidence of alcohol or drug abuse, within the 12 months before screening or a positive drug screen for amphetamines, cocaine, methadone or opiates at screening unless it can be explained by a prescribed medication; the diagnosis and prescription must be approved by the investigator. Screening results must be reviewed by the investigator to confirm eligibility prior to dosing.
- 14. Known hypersensitivity or contraindication to an siRNA or GalNAc
- 15. History of intolerance to SC injection
- 16. Any conditions which, in the opinion of the investigator, would make the subject unsuitable for enrollment or could interfere with the subject's participation in or completion of the study
- 17. Donated more than 500 mL of blood within 90 days before study drug administration
- 18. Creatinine clearance (CLcr) < 60 mL/min as calculated by the Cockcroft-Gault formula at screening
- 19. History of chronic liver disease from any cause other than chronic HBV infection
- 20. History of hepatic decompensation, including ascites, hepatic encephalopathy and/or esophageal or gastric varices

#### 6. INVESTIGATIONAL MEDICINAL PRODUCTS

## 6.1. Randomization, Blinding, and Treatment Codes

An Interactive Web Response System (IWRS) will be employed to manage subject randomization and treatment assignments.

### 6.1.1. Procedures for Breaking of Treatment Codes

Blinding of study treatment will be managed by the clinical investigative site's pharmacy in accordance with the Pharmacy Manual. In the event of a medical emergency where breaking the blind is required to provide medical care to the subject, the investigator may obtain treatment assignment for that subject. IWRS should be used as the primary method of breaking the blind. If IWRS cannot be accessed, the investigator should contact the Sponsor medical monitor to break the blind. Treatment assignment should remain blinded unless that knowledge is necessary to guide subject emergency medical care. The investigator is requested to contact the Sponsor medical monitor promptly in case of any treatment unblinding.

Blinding of study treatment is critical to the integrity of this clinical study and therefore, if a subject's treatment assignment is disclosed to the investigator, the subject will have study treatment discontinued. All subjects will be followed until study completion unless consent to do so is specifically withdrawn by the subject.

The Sponsor or designee may independently unblind cases for expedited reporting of suspected unexpected serious adverse reactions (SUSARs) as required by regulators.

#### 6.2. Description and Handling of VIR-2218 and Placebo

#### **6.2.1.** Formulation

VIR-2218 is a clear, colorless to pale yellow solution, which will be supplied by the Sponsor as a sterile solution for SC injection at a free acid concentration of 200 mg/mL. Placebo is a sterile, preservative-free normal saline 0.9% solution for SC injection, which will be supplied by the clinical investigative site or the Sponsor where required.

### 6.2.2. Packaging and Labeling

VIR 2218 (solution for SC injection) is packaged in 2-mL glass vials with a fill volume of no less than 0.7 mL to allow for complete withdrawal of 0.5 mL of drug product at the pharmacy. The container closure system consists of a Type I glass vial, a Teflon-faced 13-mm stopper, and a flip-off aluminum seal.

VIR-2218 and Placebo will be packaged and labeled in a manner consistent with the study design and applicable regulations.

#### 6.2.3. Storage and Handling

Study drug may be dispensed only by the investigator, by a staff member specifically authorized by the investigator, or by pharmacy staff, as appropriate.

Each clinical investigative site will be responsible for assembly and labeling of injection syringe(s) according to procedures detailed in the Pharmacy Manual. The pharmacy staff will prepare the study drug using an aseptic technique. The amount (in mg) of study drug to be administered will be determined based on the assigned dose level for the cohort for subjects with chronic HBV infection. All syringes will be covered to ensure the study blind is maintained since the IP solution may have a slight yellow coloring and the placebo (sterile normal saline) is clear. Additional details regarding the procedure for preparing study drug, the volume to be loaded into each syringe, and how the syringes are to be 'blinded' are provided in the Pharmacy Manual.

No special procedures for the safe handling of VIR-2218 are required. Study drug will be stored upright and refrigerated at 2 to 8°C protected from light in the storage area of the clinical investigative site pharmacy, in a secure, temperature-controlled, locked environment with restricted access. Any deviation from the recommended storage conditions should be reported to the Sponsor and use of the study drug halted until authorization for its continued use has been provided by the Sponsor or designee. Refer to the Pharmacy Manual for additional storage details.

## 6.2.4. Dosage and Administration of VIR-2218

Dose and dose cohorts for this study are described in Sections 1.2.4 and 4.1, respectively. Study drug dose and administration are summarized by dose cohort in Table 4. On dosing days, the pharmacist or designee will withdraw the required amount of study drug into 1 or more syringes containing up to 1.5 mL/ syringe. A qualified clinical investigative site staff member under the supervision of the investigator or designee will administer study drug to subjects via SC injection. The injection site(s) will be marked and mapped for later observation and should be documented. If a local reaction around the injection site occurs, photographs may be obtained. Refer to the Pharmacy Manual for detailed study drug preparation and administration instructions.

**Table 4.** Study Drug Dose and Administration

Cohort	Visit Dose Level (mg)	Visit Dose Volume (mL)	Cumulative Dose (mg)	Injections Per Dose Administration	Injections Total	Cumulative Dose Volume (mL)
Part One						
Low dose	50	0.25	100	1	2	0.50
High dose	100	0.50	200	1	2	1.0
Optional	≤ 200	≤ 1.0	≤ 400	1	2	≤ 2.0
Part Two						
Low dose	50	0.25	100	1	2	0.50
High dose	100	0.50	200	1	2	1.0
Optional	≤ 200	≤ 1.0	≤ 400	1	2	≤ 2.0

## 6.3. Investigational Product Accountability

The investigator or designee will maintain accurate records of receipt and the condition of the study drug supplied for this study, including but not limited to, date of receipt, quantity, and temperature. In addition, accurate records will be kept of when and how much study drug is dispensed and administered to each subject in the study. Any reasons for departure from the protocol dispensing regimen must also be recorded.

At the completion of the study, there will be a final reconciliation of all study drugs.

Further instructions about drug accountability and disposal are detailed in the Pharmacy Manual.

## 6.4. Concomitant Therapy

#### **6.4.1.** Permitted Concomitant Medications

The following medications/treatments are permitted:

- Hormone replacement therapy
- Oral, injectable, subdermal, intravaginal, or implantable contraceptives, as well as
  intrauterine device, and intrauterine hormone-releasing system are permitted for
  contraception
- Paracetamol ( $\leq 2g/day$ ), aspirin ( $\leq 3g/day$ ), or ibuprofen (< 1.2 g/day)
- Antihistamines
- Prescription inhaler or nebulizer to treat asthma (inhaled bronchodilator or inhaled steroid). Asthma must be well controlled, defined as historical use of a rescue bronchodilator on average no more than twice per week.

• A stable dose and regimen of any medication(s) (prescription or OTC) that the subject is taking regularly (i.e. medications for chronic conditions such as hypertension, high cholesterol, or depression must be unchanged in dose or type for at least 6 months), is permitted, except those listed in Section 6.4.2.

Investigators may initiate new prescription and non-prescription concomitant medications or treatments deemed necessary to provide adequate care for AEs or other new onset medical conditions, except those listed in Section 6.4.2.

#### 6.4.2. Prohibited Concomitant Medications

The following medications/treatments are prohibited:

- Any OTC medications or herbal remedy within 14 days before Day 1 and throughout the study, except for those specified in Section 6.4.1
- Any prescription medications within 14 days before study drug administration except for those specified in Section 6.4.1 and NrtI therapy

## 6.5. NrtI Therapy

Examples of allowed NrtI therapy are listed below, but not limited to:

- Tenofovir (tenofovir alafenamide (TDF) or tenofovir disoproxil fumarate (TAF) at recommended dose for the given tablet)
- Entecavir
- Lamivudine
- Adefovir/adefovir dipivoxil

## 6.6. Contraceptive Requirements

WOCBP may be included in this study and include any female subject who has experienced menarche and who is not post-menopausal or permanently sterilized (eg, bilateral tubal occlusion, hysterectomy, or bilateral salpingectomy).

WOCBP must be willing to use highly effective methods of contraception 14 days before dose, throughout study participation, and for 12 weeks after last dose of study drug administration. Highly effective methods of birth control result in a low failure rate (ie, less than 1% per year). Birth control methods which are considered highly effective include:

• Established use of combined (estrogen and progestogen containing) oral, intravaginal, or transdermal hormonal methods of contraception associated with inhibition of ovulation **OR** established use of progestogen-only oral, injectable, or implantable

hormonal methods of contraception associated with inhibition of ovulation. It is not currently known whether VIR-2218 will impact the effectiveness of hormonal contraceptive methods; therefore, it is recommended to use an additional form of contraception (ie, barrier method) throughout the study and for 12 weeks after last study drug administration.

- Placement of an intrauterine device
- Placement of an intrauterine hormone-releasing system
- Surgical sterilization of male partner (with the appropriate post-vasectomy documentation of the absence of sperm in the ejaculate; for female subjects on the study, the vasectomized male partner should be the sole partner for that subject)
- True sexual abstinence, when in line with the preferred and usual lifestyle of the subject. Periodic abstinence (e.g., calendar, ovulation, symptothermal, post-ovulation methods) and withdrawal are not acceptable methods of contraception. Abstinent subjects have to agree to use 1 of the above-mentioned contraceptive methods, if they start sexual relationships during the study and for up to 12 weeks after last dose of study drug administration, or for as long as the subject is followed on study, whichever is longer.
- Barrier method in combination with hormonal contraceptive, as described above

Post-menopausal status is defined as 12 months with no menses without an alternative medical cause.

Male subjects with female partners of child-bearing potential must agree to meet 1 of the following contraception requirements from the time of study treatment administration until the last follow-up visit.

- Vasectomy with documentation of azoospermia
- Male condom plus partner use of 1 of the contraceptive options listed above for contraception for WOCBP (hormonal contraceptive, intrauterine device)

Male subjects must also agree not to donate sperm for the 12 weeks following last study drug administration.

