## PROTOCOL SYNOPSIS

A Phase 2 Randomized, Placebo-Controlled Study in Mainland China to Evaluate the Safety, Tolerability, Pharmacokinetics and Antiviral Activity of VIR-2218	
Planned to be conducted at multiple clinical investigative sites in mainland China.	
Phase 2	
Up to 30 subjects	
Up to 30 adult subjects with HBeAg-negative or HBeAg-positive chronic hepatitis B virus (HBV) without cirrhosis on nucleos(t)ide reverse transcriptase inhibitor (NrtI) therapy.	
Adult subjects with chronic HBV infection without cirrhosis on NrtI therapy.	
Inclusive of screening to post-dose follow-up, the estimated total time on study for each subject is up to 20 weeks: screening period (4 weeks), dosing period (4 weeks) and post-dose follow-up period (12 weeks).	
Additional HBsAg monitoring is required for subjects with a $\geq 1$ $\log_{10}$ change from baseline (Day 1 predose level) decrease in HBsAg achieved by the Week 16 visit. Subjects will be followed until the HBsAg level returns to $> 90\%$ of the Day 1 predose level or Week 48, whichever comes earlier. Additional HBsAg monitoring may be discontinued at the Sponsor's discretion based on emerging data.	
Post-dose follow-up period:	
All subjects will be followed until Week 16.	
Extended follow-up period:	
Extended follow-up visits will occur every 4 weeks starting at Week 20 and up to Week 48.	

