#### 8.3.1. Adverse Events

Following initiation of study medication, collect all AEs, regardless of cause or relationship, until 12 weeks after last administration of study drug.

All AEs should be followed up until resolution or until the AE is stable, if possible. Sponsor may request that certain AEs be followed beyond the protocol-defined follow-up period.

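### Male contraception ends at the last follow-up visit with no minimum time after the last dose, so it can end before the 12-week sperm-donation ban on the same men

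*Protocol*

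**What the plan says.** Protocol Section 6.6 ties men with partners of child-bearing potential to "contraception requirements from the time of study treatment administration until the last follow-up visit". Section 5.2, inclusion criterion 4, uses the same end point: "from the time of study drug administration until the last follow-up visit". Neither place states a minimum time after the last dose.

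The neighbouring rules are anchored to dosing. On sperm donation, Section 6.6 reads: "Male subjects must also agree not to donate sperm for the 12 weeks following last study drug administration". For women of child-bearing potential, contraception runs "throughout study participation, and for 12 weeks after last dose of study drug administration".

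The visits that could be a man's last are set elsewhere:

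- The Synopsis, on post-dose follow-up: "All subjects will be followed until Week 16". Only subjects with a sufficient HBsAg decline continue to Week 20 and beyond.
- Section 4.2, on leaving early: "If a subject discontinues from the study post-dose but before completion of the Week 16 visit, an Early Termination (ET) visit should be performed". The same section says: "Subjects who discontinue prematurely will be followed for safety", with no duration.
- Appendix 2 places ET in the Week 16 column. The second dose is at Day 29 ± 2 and Week 16 at Day 113 ± 7.
- Section 8.3.1 collects adverse events "until 12 weeks after last administration of study drug".

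**The concern.** The male contraception duty is the only one of these precautions tied solely to a visit. A visit can fall early within its window, or be brought forward when a subject leaves. A man can then be released from contraception while the protocol still bars him from donating sperm. Conception with a partner is the more direct route to pregnancy, so the shorter period would apply where the longer one might be expected.

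Two groups could fall short. The first is early leavers with no visit after ET: the text does not say whether ET is the last follow-up visit, so site staff must choose between two end dates. The second is men who complete Week 16 and do not enter extended follow-up. For them the shortfall arises from the visit windows alone, whichever way ET is read.

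What is at stake is consistency of a safety precaution. No endpoint, analysis set or estimate depends on it.

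**Working it through.** **Inputs.** First dose Day 1; second dose Day 29 ± 2, so Days 27–31; Week 16 at Day 113 ± 7, so Days 106–120; Week 20 at Day 141 ± 7 (all from Appendix 2). Precaution period 12 weeks = 84 days (the sperm-donation rule in Section 6.6).

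**Formula.** Shortfall = 84 − (day of last visit − day of last dose), or 0 if that is negative.

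**The plan's own figure.** Section 4.1 gives a 12-week follow-up after the second dose. At nominal days, 113 − 29 = 84 days, which reproduces it with no margin.

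**Completers not in extended follow-up.** There are 5 × 15 = 75 allowed day pairs.

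| Second dose | 12-week date | Week 16 days that fall short | Pairs short | Sum of shortfalls (days) |
|---|---|---|---|---|
| Day 27 | Day 111 | 106–110 | 5 | 15 |
| Day 28 | Day 112 | 106–111 | 6 | 21 |
| Day 29 | Day 113 | 106–112 | 7 | 28 |
| Day 30 | Day 114 | 106–113 | 8 | 36 |
| Day 31 | Day 115 | 106–114 | 9 | 45 |
| Total | | | 35 | 145 |

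So 35 of 75 pairs fall short, by 1 to 9 days, with a mean over those pairs of 145 / 35 = 4.1 days. The worst case is 106 − 31 = 75 days of cover, and 84 − 75 = 9 days short. With the second dose exactly on Day 29, the maximum is 84 − (106 − 29) = 7 days.

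**Early leavers, if ET is the last follow-up visit.**

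| Doses received | 12-week date | ET day | Days short |
|---|---|---|---|
| Two (Days 1 and 29) | Day 113 | 36 | 113 − 36 = 77 |
| Two | Day 113 | 57 | 113 − 57 = 56 |
| Two | Day 113 | 85 | 113 − 85 = 28 |
| Two | Day 113 | 113 | 0 |
| One (Day 1) | Day 85 | 8 | 85 − 8 = 77 |
| One | Day 85 | 29 | 85 − 29 = 56 |
| One | Day 85 | 85 | 0 |

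The ET days are illustrative.

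**Early leavers, if scheduled Week 16 (Day 113) is meant.** There is no shortfall with the second dose on Days 27–29, 1 day on Day 30 (113 − 30 = 83) and 2 days on Day 31 (113 − 31 = 82).

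**Men not affected.** A one-dose man who stays to Week 16 has at least 106 − 1 = 105 days. A man seen at Week 20 or later has at least 134 − 31 = 103 days.

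**Numbers of subjects.** The trial has at most 30. The documents give no dropout rate or sex split. Assuming 0–10% leave early, that is 0–3 subjects, before restricting to men with partners of child-bearing potential.

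**The case against.** The strongest counter-argument is that the protocol already shows what it intends. Section 8.5.2 describes the follow-up period for pregnancy reporting as lasting 12 weeks from the last dose, and asks men to report partner pregnancies through the follow-up period. Section 4.1 gives the same length. On that view the last follow-up visit is simply the one that closes a 12-week period, and ET's place in the Week 16 column says only which assessments are done. This is good evidence of intent, but it defines a reporting period and not the visit at which contraception ends. It also means partner pregnancies can still be reportable after the man has been released.

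The multi-week shortfall needs several things at once: ET counts as the last visit, the man has no later visit, and he leaves within 12 weeks of his last dose. Section 4.2 promises safety follow-up, Section 8.3.1 runs adverse event collection to 12 weeks, and Section 6.1.1 keeps unblinded subjects in follow-up unless they withdraw consent. That narrows the group to men with no visit after ET; stopping study drug alone does not put a man in it. None of these provisions guarantees a contact at 12 weeks.

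The completer shortfall can fairly be called ordinary window tolerance, and the 35 of 75 weights all day pairs equally. Both points stand, and both bear on weight. It is also fair that no hazard is shown (nonclinical data are left to the Investigator's Brochure), that nothing in the documents requires the donation and contraception periods to match, and that a vasectomised man is unaffected in practice.

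**Conclusion.** The point holds, at minor severity. Followed exactly, the written rule can release a dosed man before the protocol's own 12-week precaution ends. The completer gap, at most 9 days, needs no disputed reading; it assumes only that Week 16 is scheduled by study day, and no text re-anchors it to the actual second-dose date. The gap of up to about 11 weeks in the examples is conditional on reading ET as the last follow-up visit and on there being no later visit. Which reading sites would apply cannot be settled from the documents.

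Whether 84 days is the right period for men cannot be judged here either. The finding is that the protocol does not guarantee, for contraception, the period it sets for sperm donation.

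**What to change.** In Section 5.2 (inclusion criterion 4) and Section 6.6, end the male contraception duty at the later of the last follow-up visit and 12 weeks after the last dose. Section 6.6 already uses a longer-of-two rule for abstinent subjects, so the device is not new to the protocol. Every dosed man then has at least 84 days, the choice of end date at ET disappears, and the longer duty for men in extended follow-up is kept. Carry the clause into the consent form if it is not already there; the consent pages were not available for review.

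The cost is one clause in two places, with no added visit, procedure or analysis. The downside is a longer obligation for a few early leavers, which cannot be checked once they have gone, and 1 to 9 more days for some completers. At nominal days nothing changes.
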